#### The secondary objectives are

- 1. To estimate the incidence of severe adverse events attributable to the intervention;
- 2. To estimate the effect of the intervention on all-cause mortality;
- 3. To estimate the costs and cost effectiveness of the intervention.
- 4. To estimate the prevalence of latent TB infection four years after the intervention among children born between 2008 and 2016,

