# 11) Adverse event reporting

# **Definition of terms**

## Adverse Event (AE)

Any untoward medical occurrence in a patient or clinical investigation subject administered a pharmaceutical product. It does not necessarily have a causal

TEST AND TREAT TO END TB Protocol, V2.0 14th September 2021 relationship with this treatment. An adverse event can be any unfavourable and unintended sign, symptom, or disease temporally associated with the use of a medicinal (investigational) product, whether or not related to the medicinal (investigational) product.

An adverse event is any adverse occurrence that occurs after study participant signs the consent form, even if it may not be directly related to the treatment.

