#### **Adverse Drug Reaction (ADR)**

Adverse event that is assessed as possibly, probably or certainly attributable to the study medication.

Adverse events that occur more than 14 days after the date of taking the last dose of the study drug will be deemed to be unrelated to the study drug.

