## Framework

The following committees, that are relevant to the patient safety and pharmacovigilance will oversee the trial:

- a) a trial management committee (TMC), comprising the senior investigators and trial management staff, who will conduct the day-to-day operations of the trial;
- b) a trial steering committee (TSC), including independent expert members and chair, who will review and approve protocols and key study documents as well as reports from the IDMC;
- c) an independent data monitoring committee (IDMC), who will review safety and efficacy data, independent of the TMC, and provide advice to the TMC and the TSC; and
- d) an expert clinical panel (ECP), who will review individual adverse event data, adjudicate event severity and attribution to study drug and report to the IDMC.

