# 12) Data analysis

Primary study objective is to estimate, among people living in Ca Mau Province, the effect of universal testing for and treatment of LTBI, together with active case finding **and treatment** for TB, on the population prevalence of **pulmonary** TB after **two** years.

The analysis will be by intention-to-treat. We will use a two-level (sub-commune and household) hierarchical generalised linear model with a Poisson error distribution to test the effect of treatment group allocation on number of prevalent cases of pulmonary TB in persons aged  $\geq 15$  years. Treatment group allocation will be the main (fixed) effect. Clusters will be treated as a random intercept term. The enumerated cluster population aged  $\geq 15$  years will be the offset. A p value < 0.05 will be treated as significant. No covariates will be included in the primary analysis. Prevalence rate ratios will be estimated with 95% confidence intervals, adjusted for clustering.

A secondary objective is to estimate the incidence of adverse events attributable to 3HP preventive therapy (safety analysis). The incidence of all adverse events grade 3 or higher, together with specific, expected adverse events in the intervention group will be enumerated and reported as rates per person-year of participation in the study.

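### Section 12 sets a safety objective of harm attributable to 3HP but fixes a measure with no attribution condition, no comparator and no exposure-based time window

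*Protocol*

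**What the plan says.** The objective appears in two forms. The Synopsis and Section 4 list, as the first secondary objective, "To estimate the incidence of severe adverse events attributable to the intervention". Section 12 words it differently: "A secondary objective is to estimate the incidence of adverse events attributable to 3HP preventive therapy (safety analysis").

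The next sentence of Section 12 gives the measure: "The incidence of all adverse events grade 3 or higher, together with specific, expected adverse events in the intervention group will be enumerated", and these are to be "reported as rates per person-year of participation in the study".

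Section 11 supplies the definitions. Under Adverse Event: "An adverse event is any adverse occurrence that occurs after study participant signs the consent form, even if it may not be directly related" (that is, related to treatment). Under Adverse Drug Reaction: "Adverse event that is assessed as possibly, probably or certainly attributable to the study medication", with a rule that events more than 14 days after the last dose are deemed unrelated. Under Framework, an expert clinical panel is to "adjudicate event severity and attribution to study drug and report to the IDMC"; Section 14 repeats this. The six-monthly safety report, also in Section 11, includes attribution for all events.

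Under Trial design in Section 6, control clusters receive routine care with no study intervention. No adverse event collection is described for them.

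**The concern.** Two consecutive sentences of Section 12 answer different questions. The first asks how much harm 3HP causes. The second counts grade 3 or higher events whatever their cause, plus pre-listed expected events, again without asking whether the drug caused them. In a population offered treatment across whole communities, some people will become seriously ill during three to four months for unrelated reasons, and those events enter the numerator.

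This is more than detail left to the statistical analysis plan. The protocol itself fixes the numerator, so a plan that followed it faithfully would inherit the mismatch. At stake is the reading of a pre-specified secondary objective: the safety of a preventive regimen given to people without active disease. The primary endpoint is not affected.

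**Working it through.** **No safety figure to reproduce.** The protocol states no rate, sample size or precision for the safety analysis. The check is a comparison of text, followed by an illustration.

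**Step 1: objective against measure.**

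| Element | Objective (Sections 4 and 12) | Measure (Section 12) |
|---|---|---|
| Cause | Attributable to the intervention (Section 4) or to 3HP (Section 12) | No condition |
| Severity | Severe (Section 4); not limited (Section 12) | Grade 3 or higher, plus specific expected events |
| Comparator | None needed if attribution is adjudicated | None, so background cannot be subtracted |
| Start of events | Exposure to 3HP is implied by attribution | Consent, which one not stated (Section 11) |
| Denominator | Exposed people or time is implied | Person-years of study participation, not defined |

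The attribution tools (the adverse drug reaction category, the 14-day rule and the panel's adjudication) are all in Section 11. Section 12 refers to none of them.

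**Step 2: the window.** Section 15 lists separate written consents, one for screening and one for evaluation and preventive treatment. Section 11 does not say which opens the adverse event window. If it is the screening consent, skin-test reading, radiography, blood tests and any wait for cultures all fall inside the window before a dose. If it is the treatment consent, the gap is shorter; Section 8 at one point places that consent at the first treatment visit. Medical review can delay treatment by up to 8 weeks, but only for people with an acute illness at that review.

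**Step 3: illustration with person-time confined to treated people.** Assumed inputs, not in the protocol: background grade 3 or higher rate *b* of 1 to 5 per 100 person-years; drug-related grade 3 or higher events in 0.2% to 2% of those treated. From Section 9, treatment ends at the 12th weekly dose or at 16 weeks, and the final visit is two weeks later, so about 14 to 18 weeks.

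Per 1,000 treated: person-years *T* = 1,000 × weeks / 52; background events *B* = *bT*; drug-related events *A* = 1,000 × proportion; background share = *B* / (*A* + *B*).

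- Middle case (14 weeks, *b* = 2, 0.5%): *T* = 269.2; *B* = 5.38; *A* = 5. All-cause rate = 10.38 / 269.2 = 3.86 per 100 person-years; attributable rate = 5 / 269.2 = 1.86. Share = 52%.
- Lowest share (14 weeks, *b* = 1, 2%): *B* = 2.69; *A* = 20. Share = 2.69 / 22.69 = 12%.
- Highest share (18 weeks, *b* = 5, 0.2%): *T* = 346.2; *B* = 17.31; *A* = 2. Share = 17.31 / 19.31 = 90%.

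**Step 4: effect of the undefined denominator.** If unexposed time is also counted, total time exceeds *T* and the reported rate is *A* / *T*(all) + *b*. Suppose, purely for illustration, that unexposed time doubles 269.2 to 538.5 person-years.

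- Middle case: 5 / 538.5 + 0.02 = 0.93 + 2.00 = 2.93 per 100 person-years, against an attributable 1.86 in exposed time.
- *b* = 1, 2%: 20 / 538.5 + 0.01 = 3.71 + 1.00 = 4.71, against 20 / 269.2 = 7.43.

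The stated rate can therefore lie above or below the attributable one. Neither its distance nor its direction is fixed by the text.

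**The case against.** The strongest reply is that attribution is well provided for. Section 11 defines it, a panel adjudicates it, and the six-monthly report tabulates it. What Section 12 lacks could be called one linking phrase, and the exact tabulation is normally left to the analysis plan. It is also reasonable, in an open-label trial, to report all grade 3 or higher events regardless of cause, because that avoids filtering by unblinded causality judgement.

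Much of this stands. The data exist, and the all-cause rate deserves to be kept. But Section 12 is not silent. It names a measure for an attributable-harm objective, and that measure does not contain attribution. Reporting all causes is a sound addition, not an answer to the question posed.

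Three stronger readings are tempting, and the documents do not support them:

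- A reader might infer that background illness is simply reported as the drug effect. The measure contains drug-related events and pre-listed expected reactions as well; it is a mixture.
- A reader might infer that unexpected reactions below grade 3 go unreported. They are outside this measure, but Section 11 requires all non-serious events to be recorded, summarised and reported, and the six-monthly report covers all adverse events with their grade.
- A reader might infer that the rate feeds the cost-effectiveness work. The protocol mentions only effectiveness and costs there.

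The absence of control-arm data is also not a fault in itself, since no 3HP reactions can arise in those clusters. It matters only because the measure has no other means of separating background events.

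**Conclusion.** The point holds as a mismatch between a stated objective and its stated measure. As written, Section 12 yields an all-cause rate, over an undefined period of participation, for a question about harm attributable to 3HP. The mixture of drug-related and background events cannot be determined from the documents. The 12% to 90% range rests wholly on assumed rates and on person-time confined to treated people; it shows that the ambiguity could matter, not how large it is. With unexposed time in the denominator, the rate could even understate attributable harm.

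The pre-dose problem is conditional: it depends on which consent starts the window, and the long delay at medical review applies to a subgroup only. This is a secondary-objective defect that should be corrected because correction is cheap; it does not threaten the trial's main conclusion.

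**What to change.** In Section 12, or in the analysis plan with a matching protocol clarification:

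1. Name as the measure for this objective the adverse drug reactions of grade 3 or higher, adjudicated by the expert clinical panel as possibly, probably or certainly attributable, among people who took at least one dose of 3HP.
2. Run both the event count and the person-time from first dose to 14 days after the last dose, in line with the existing rule in Section 11.
3. Keep the all-cause grade 3 or higher rate and the specific expected events as separate descriptive lines, each with its own defined period. State which consent opens the adverse event window, and show pre-dose events apart.
4. Reconcile the objective: the Synopsis and Section 4 speak of severe events and the intervention, while Section 12 speaks of adverse events and 3HP.

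The cost is mainly wording. Attribution is already adjudicated, and the weekly delivery date and the method of administration are already recorded. Where treatment is self-administered, the dispensing date would have to stand in for the dosing date, and that should be stated. The one real downside is reliance on causality judgements made without blinding; the retained all-cause line offsets it.

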## Assessment for LTBI treatment phase

#### Evaluation at central location

Participants who have a positive TST or who report symptoms of TB will be asked to have:

 A chest Xray in a mobile x-ray van located at central location, in or near their village. Images will be exported to our online data repository. Images will either be read by an onsite radiologist or initially assessed using a validated artificial intelligence program for detection of TB. In the latter case, those images flagged as abnormal will be re-read by an onsite radiologist (see "Chest radiograph report form"). Chest xrays will be classified by each reader as: "consistent with TB", "abnormality, other than TB" and "normal or no significant abnormality". Women who state they are pregnant or attempting to fall pregnant will be excluded from chest radiography.

2. Baseline measurement of body weight, blood pressure and blood tests for liver function tests (LFT), full blood count (FBC). The physical examination findings will be recorded on the "Body weight, Blood Pressure forms".

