#### Monitoring for adverse events

Participants who meet one or more of the following criteria

- aged  $\geq$  45 years,
- have baseline AST or ALT higher than normal (but less than three times the upper limit of normal), OR
- are flagged by the trial doctor for the high-risk monitoring for adverse event

will have liver function tests repeated at two weeks, at four weeks after commencement of treatment and then at four weekly intervals throughout treatment.

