#### For participants in high-risk risk stratum group in Weeks 2, 4, 8, 12, 16 only

- Collect one biochemistry blood tube for liver function test.
- Record collection date and time in eCRF
- Despatch to laboratory
- Record results in eCRF. The sample should arrive to lab within 24 hours at a suitable temperature.

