## Expected adverse drug reactions

This will be based on registered product information for isoniazid and on the Investigators Brochure for rifapentine. Currently, these identify the following adverse effects as expected with the study drugs.

Rifapentine*	Isoniazid
Hypersensitivity reactions	Hepatitis
Hepatotoxicity	

astrointestinal ymptoms
eripheral neuropathy
nmunologic reactions
e

\* The following additional adverse events have also been observed when rifapentine has been taken in combination with other anti-TB drugs: neutropenia, lymphocytopenia and anaemia.

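### The rate of laboratory-defined liver injury is planned over the whole intervention group, although scheduled on-treatment liver tests are confined to the high-risk stratum, so it is biased downward by an amount the protocol does not determine

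*Protocol*

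**What the plan says.** The safety paragraph of section 12, Data analysis, covers all adverse events of grade 3 or higher and adds that "specific, expected adverse events in the intervention group will be enumerated and reported as rates per person-year of participation in the study". It does not separate monitoring strata, or events found by blood test from events found through symptoms.

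The table under Expected adverse drug reactions lists "Hepatotoxicity" for rifapentine and hepatitis for isoniazid. The section on adverse events of special interest names hepatotoxicity again.

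Liver function is tested at baseline in everyone assessed at the central location. After that, under Monitoring for adverse events, three groups "will have liver function tests repeated at two weeks, at four weeks after commencement of treatment" and every four weeks from then on: those aged 45 or over, those who "have baseline AST or ALT higher than normal (but less than three times the upper limit of normal), OR" those who "are flagged by the trial doctor for the high-risk monitoring for adverse event". The later instruction to "Collect one biochemistry blood tube for liver function test" stands under a heading that confines it to the high-risk stratum at weeks 2, 4, 8, 12 and 16. All other treated participants answer a symptom checklist before each dose and at the final visit, with no scheduled liver test.

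**The concern.** A rate needs a denominator made up of people in whom the event could have been recorded. A treated participant aged 5 to 44 with normal baseline transaminases and no flag contributes person-time throughout, but a symptomless transaminase rise in that person has no scheduled route into the data. The planned figure therefore mixes a laboratory-monitored rate with a symptoms-only rate.

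This matters because the absolute rate is itself the safety estimate. Control clusters receive no study intervention and section 12 tabulates adverse events in the intervention group only, so no comparison between arms could cancel the incomplete ascertainment. The trial treats a general population from age 5 and aims to inform wider use, where liver safety is a central question. The mixed rate would also move with the age mix of those treated, even if the drug's risk at each age stayed the same.

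**Working it through.** The protocol states no hepatotoxicity rate, stratum size or safety precision, so there is no figure to reproduce. The direction follows from the text. The size can only be illustrated.

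**From the protocol**
- Who is tested on treatment: the high-risk stratum only.
- How others are followed: symptom checklist before each dose and at the final visit.
- What is counted: grade 3 or higher events and specific expected events, which include hepatotoxicity.
- Denominator: person-years of participation in the intervention group.

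**Assumed, because the protocol does not give them**
- h, the share of treated person-time under scheduled liver testing: 0.3 to 0.7.
- r, the true liver-injury rate in the untested stratum divided by that in the tested stratum: 0.1 to 1.
- s, the share of injury in the untested stratum that stays silent and so goes unrecorded: 0.3 to 0.8, with 1 as the extreme case.
- Scheduled tests find all injury in the tested stratum. This is generous, since tests two to four weeks apart can miss some.

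**Formula.** Set the tested stratum's true rate to 1.

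True overall rate = h + (1 − h)r

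Observed overall rate = h + (1 − h)r(1 − s)

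Shortfall = 1 − observed/true = (1 − h)rs / [h + (1 − h)r]

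The shortfall is above zero whenever h < 1, r > 0 and s > 0.

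| h | r | s | True | Observed | Observed/true | Shortfall |
|---|---|---|---|---|---|---|
| 0.7 | 0.25 | 0.3 | 0.775 | 0.7525 | 0.97 | 3% |
| 0.5 | 0.1 | 0.5 | 0.55 | 0.525 | 0.95 | 5% |
| 0.5 | 0.2 | 0.5 | 0.60 | 0.55 | 0.92 | 8% |
| 0.5 | 0.1 | 1 | 0.55 | 0.50 | 0.91 | 9% |
| 0.5 | 0.5 | 0.5 | 0.75 | 0.625 | 0.83 | 17% |
| 0.5 | 0.5 | 1 | 0.75 | 0.50 | 0.67 | 33% |
| 0.3 | 0.5 | 0.8 | 0.65 | 0.37 | 0.57 | 43% |
| 0.3 | 1 | 0.8 | 1.00 | 0.44 | 0.44 | 56% |

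With the tested stratum reported alone over its own treated person-time, numerator and denominator match. Under the same assumption of complete detection, the ratio is then 1 for that stratum.

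Restricting the denominator to time on treatment would not remove this bias, because the untested stratum also takes 3HP. Whether person-years of participation reach beyond treated time is a separate question and is not part of this point.

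**The case against.** Section 12 neither names hepatotoxicity in its rate sentence nor calls the rate pooled. It speaks of rates in the plural, and an analysis plan that is not shown could split them by stratum. The untested stratum is also selected to be at low risk: it excludes older participants and those with raised baseline tests, and known liver disease, regular medication or heavy alcohol use leads to a medical review at which the stratum can be changed. A small r is what the design intends. Weekly symptom screening will find some low-risk events, so taking all of them as silent is extreme. The tabulation is descriptive, has no bearing on the primary endpoint, and the data monitoring committee separately receives six-monthly reports of all adverse events.

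Most of this stands as a limit on size and importance. It does not remove the mismatch. The section itself fixes the group and the denominator, and followed as written it divides by person-time in which silent injury cannot be seen. That is more than detail left for later.

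A reader might infer that no overall rate should be given, or that the tested stratum's rate is the right figure for a general population. The documents support neither. That stratum is chosen for higher risk, so its rate is not a general-population rate. An overall rate under the monitoring as delivered is legitimate if it is labelled as such.

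**Conclusion.** The point holds for liver injury that is laboratory-defined and without symptoms. Its planned rate is biased downward whenever any such injury occurs in untested participants. That direction needs no assumption about stratum size, only that the untested stratum is not empty.

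The size is not known. Under the assumed inputs it is small, about 3 to 10%, when the untested stratum is small or at low risk; 17% in a middle case (h, r and s all 0.5); and 56% in the least favourable case with s at 0.8.

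Two stronger readings should be resisted. A reader might infer that the understatement is usually 10% or more, but a count of table rows reflects the values chosen for h, r and s, none of which the protocol gives; with r at 0.1 and h at 0.5 the shortfall stays under 10% even if every low-risk event is silent. A reader might also infer that clinically apparent liver harm goes uncounted in the untested stratum. The protocol seeks symptoms in all treated participants, so symptomatic hepatitis is not affected in this way.

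This is a defect in a secondary, descriptive safety estimate. It is worth correcting because the correction is nearly free.

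**What to change.** In the safety paragraph of section 12:

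- Report laboratory-detected liver events (hepatotoxicity and transaminase elevations of grade 3 or higher) by monitoring stratum. For the high-risk stratum, use treated person-time under scheduled liver testing as the denominator.
- Report symptomatic or clinically diagnosed hepatitis for all treated participants, also by stratum.
- If an overall hepatotoxicity rate is given, label it as the rate observed under risk-based monitoring, and do not present it as the full incidence of liver injury under 3HP.
- State that the high-risk-stratum rate does not by itself represent the general population.

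No change to clinical monitoring is proposed. Age and baseline transaminases are already collected, and on-treatment test dates and results are recorded in the eCRF; the doctor's flag needs to be carried into the analysis dataset. The cost is some wording and one extra split in the safety tables. The downside is a laboratory-based liver rate that applies only to the monitored stratum and may look higher.
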